THIS PROTOCOL AMENDMENT AND ALL OF THE INFORMATION RELATING TO IT ARE CONFIDENTIAL AND PROPRIETARY PROPERTY OF MERCK SHARP & DOHME CORP., A SUBSIDIARY OF MERCK & CO., INC., WHITEHOUSE STATION, NJ, U.S.A.

This protocol amendment is applicable only to France.

SUMMARY OF CHANGES

PRIMARY REASON FOR THIS AMENDMENT:

This study (PN017-21) is a long term safety extension of the base protocol, PN017-19 for use in locations that require separate documents. For locations that do not require separate documents, protocol PN017-17 is used, which includes the base protocol and the extension in one protocol.

Section Number(s)	Section Title(s)	Description of Change(s)	Rationale
2.2 7.1 7.6	Trial Flow Chart Overall Trial Design Trial Procedures	Added pharmacokinetic (PK) visits at weeks 4 and 13 of the extension (ie, weeks 82 and 91 from randomization visit in main study) Added PK sample collection to trial procedures.	Added two PK collections to this extension protocol to facilitate robust PK and PK/PD modeling for the MK-8931 program. In the base protocol, both plasma and dried blood spot (DBS) samples were collected initially for assessment of PK, but plasma sampling was dropped when preliminary analyses indicated that DBS samples were sufficient. However, due to quality issues identified with some DBS samples in the base protocol; dual sample collection (plasma and DBS) is being reinstated for the PN017 protocols. These two additional PK time points are being added to offset some of the collected DBS samples with quality issues.
2.0	Synopsis	Added note that Sponsor will be unblinded following the completion of the initial 78-week trial but some Sponsor	Maintaining Sponsor blinding for efficacy data collected at 24 months in the long-term trial is needed to support the

Section Number(s)	Section Title(s)	Description of Change(s)	Rationale
5.3	Trial Design Rationale	personnel will remain blinded during the long-term trial, as necessary, to support the conduct of the trial and the collection of efficacy data.	primary efficacy objective for the long-term trial

ADDITIONAL CHANGE(S) FOR THIS AMENDMENT:

Section Number(s)	Section Title(s)	Description of Change(s)	Rationale
2.2	Trial Flow Chart for Long Term Safety Trial	Added the following to footnote ‘j’ for dermatology: “or who have >6 month gap in study therapy between Visit 10 and 10B”.	Text in footnote was inadvertently missed out from previous amendment
2.2	Trial Flow Chart for Long Term Safety Trial	Added the following text to footnote “b” in flowchart: “However, if waiting for test results from Visit 10B is necessary in the judgment of the investigator, Visit 10B procedures can be performed over more than one visit but ideally should not exceed a 2-week timeframe. Trial medication is to be dispensed on the last day of Visit 10B.”	Added to ensure assessments are performed for subjects with extensive gap between end of main study and starting of extension
2.2	Trial Flow Chart for Long Term Safety Trial	Added the following text to footnote “c” in flowchart and added assessments to Visit 10B: C-SSRS, ECG, directed Physical Exam, Recording of Concomitant Medications should be performed and Vital Signs, Body Weight and Laboratory samples (including urinalysis) should be collected for subjects with >3 month gap in therapy between Visit 10 and 10B. The timing of Visit 11 and all subsequent visits should be based on the trial dispensing date at Visit 10B	Added to ensure assessments are performed for subjects with extensive gap between end of main study and starting of extension

Section Number(s)	Section Title(s)	Description of Change(s)	Rationale
2.2	Trial Flow Chart for Long Term Safety Trial	Added the following to Visit 10B: Issue/Collect Subject Identification Card	This is mandatory in France
7.1	Overall Trial Design	
Removed statement about ophthalmology examination completed during the Week 182 visit as this will not be done.
 
Added reference to rater manual and deleted mention of specific scales in statement describing audio-recording procedures.
	
Clarification of previous clerical error and inconsistency with flow chart
 
Clarification to ensure consistency with rater manual.

7.2	Beginning and End of the Trial	Added the following statement: Given the exploratory nature of the extension trial endpoints, the retrieved dropout approach employed in the main cohort/safety cohort trial period (initial 78 week treatment period), will not be applicable to this extension trial period. Thus, subjects who discontinue study medication during the extension trial period will be discontinued from the study.	Clarification
7.7.2.2.3	Events of Clinical Interest	Since routine MRI monitoring for safety has been discontinued, the central Reading Center is not automatically performing central reading for safety. Therefore, during the main study and the extension, the site investigator or	Clarification

Section Number(s)	Section Title(s)	Description of Change(s)	Rationale
		
radiologist should perform a local reading, as necessary. In some cases, central reads for safety may be performed. In the event that an ARIA is detected, then the Sponsor may request that the MRI be submitted for central reading.
	
8.2.7	Accounting for Missing Data	
For the Tipping Point sensitivity analysis, stated intention to calibrate between the primary ANCOVA model and the multiple imputation model, if needed.
 
Also, removed an errant negative sign from the exponent in the tipping point test statistic.
	
The tipping point sensitivity analysis is intended to report the value c that would need to be applied to all multiply-imputed values from the active arms, to turn a significant result, non-significant. However, it is possible that a slight difference may exist between the primary ANCOVA model and the multiple imputation (MI) model (absent any adjustment to the active arms) for the final observed dataset. Such a difference would bias the intended interpretation of c (i.e. some small fraction of c would represent the difference between the models, as opposed to the entirety of c representing the detrimental effect needed to be applied to the active arms to tip the significant result to non-significant.)

2.0 SYNOPSIS

TITLE OF TRIAL: A, Parallel-Group, Double Blind Long Term Safety Trial of MK-8931 in Subjects with Alzheimer's Disease. (Protocol No. MK-8931-017-21) (also known as SCH 900931, P07738)
ABBREVIATED TITLE: A Long Term Safety Trial of MK-8931 in AD (EPOCH)
OBJECTIVES: Primary Trial Objectives: 
1. To evaluate the safety and tolerability of MK-8931 in the long term treatment of mild to moderate Alzheimer's Disease2. To compare the efficacy of MK-8931 on cognition and functional ability in activities of daily living in subjects with mild to moderate AD in subjects administered MK-8931 for 24 months to that of subjects administered placebo for 18 months followed by MK-8931 for 6 months. Exploratory Trial Objective: To compare the efficacy of MK-8931 administered to subjects for 18 months to that of subjects administered placebo for 18 months during the initial 78 week trial followed by long term treatment of MK-8931 during the long term safety trial on cognition, function, disease progression, and health economic burden at multiple time points.
Trial Design Overview: This is a long-term safety study (up to approximately 260 weeks) which will be available to subjects who have completed the initial 78 week trial of MK-8931 Protocol 017. The initial 78 week trial is a double blind, placebo controlled trial to evaluate the efficacy of β -site amyloid precursor protein (APP) cleaving enzyme (BACE) inhibitor MK-8931 as a potential disease-modifying therapy in subjects with mild to moderate AD. The trial is powered to detect a clinically significant change in the two coprimary outcome measures (the Alzheimer's Disease Assessment Scale Cognitive subscale [ADAS-Cog] and the Alzheimer's Disease Cooperative Study Activities of Daily Living Inventory [ADCS-ADL] change-from-baseline scores at Week 78). At the end of the initial 78-week trial, subjects who have completed treatment may choose to participate in this long term safety trial, during which all subjects who received placebo during the initial 78 week trial will receive active drug. The long term safety trial will start with enrollment of the first subject who completes the initial 78 week trial and chooses to participate in the long term safety trial. The long term safety trial will end when the drug either becomes commercially available or when the MK-8931 program is terminated (or less, based on local regulation). The long term safety trial is expected to have a duration of up to approximately 260 weeks (5 years) for the first subject enrolled. Trial Governance: An independent eDMC will have the primary responsibility for monitoring safety throughout the trial. Treatment Arms: MK-8931 12 mg and 40 mg treatment assignments from the initial 78 week trial will be carried forward into the long term safety trial. Subjects originally on placebo will be assigned to the 40 mg dose. The Sponsor will be unblinded following the completion of the initial 78 week trial. Sites and subjects will remain blinded during the long term safety trial. Some Sponsor personnel will remain blinded during the long-term trial, as necessary, to support the conduct of the trial and the collection of efficacy data. Sample Size: The enrollment target for the initial 78 week trial is 1960 subjects. It is expected that 70% of subjects will complete the initial 78 week trial, and it is estimated that 90% of those will elect to enroll in the long term safety trial, with $(1960 * 0.70 * 0.90)$ 1235 subjects projected to enter the long term safety trial.
Number of Trial Centers: Approximately 190-210.
Duration of Participation: Expected maximum duration of approximately 260 weeks (5 years), with the duration of individual subject participation dependent on the timing of enrollment. Duration of participation may be limited based on local

TITLE OF TRIAL: A, Parallel-Group, Double Blind Long Term Safety Trial of MK-8931 in Subjects with Alzheimer's Disease. (Protocol No. MK-8931-017-21) (also known as SCH 900931, P07738)

regulations. Subjects who do not complete initial 78 week trial of MK-8931 protocol 017 will not be permitted to continue in the long term safety trial.

Duration of Trial:

The duration of the long term safety trial is expected to be up to approximately 5 years or until MK-8931 becomes commercially available or the MK-8931 program is terminated. Duration of the trial may be limited based on local regulations.

Key Inclusion Criteria:

Each subject must have tolerated study medication and completed the initial 78-week trial. Subjects who did not complete the initial 78 weeks with study medication but did continue in the trial and completed the scheduled visits, may be permitted to enroll in the long term safety trial.

Each subject must have a trial partner who is reliable and competent. The trial partner must have a close relationship with the subject, have face to face contact at least 3 days/wk for a minimum of 6 waking hours/wk (or more, based on local requirements), be willing to accompany the subject to all trial visits, and be willing to monitor compliance of the administration of the trial medication. The trial partner should understand the nature of the trial and adhere to trial requirements (eg, dose, visit schedules, and evaluations). It is recommended that the trial partner accompany the subject to all trial visits.

Key Exclusion Criteria:

The subject is at imminent risk of self-harm, based on clinical interview or on the Columbia Suicidality Severity Rating Scale (C-SSRS), or of harm to others in the opinion of the investigator. Subjects must be excluded if they report suicidal ideation with intent, with or without a plan (eg, suicidal ideation item 4 or 5 on the C-SSRS) in the past 1 month or suicidal behavior in the past 6 months.

The subject has developed a recent or ongoing, uncontrolled, clinically significant medical condition (such as, but not limited to, diabetes, hypertension, thyroid or endocrine disease, congestive heart failure, angina, cardiac or gastrointestinal disease, dialysis, or abnormal renal function with estimated creatinine clearance < 30 mL/min) other than Alzheimer's disease such that, in the judgment of the investigator, participation in the trial would pose a significant medical risk to the subject. Controlled co-morbid conditions (including diabetes, hypertension, heart disease, etc) are not exclusionary if stable. All concomitant medications, supplements (eg Vitamin E), or other substances must be kept as stable as medically possible during the trial.

Note: urinary tract infections at screening are not exclusionary if adequately treated (as documented by repeat urinalysis).

The subject has a history of, or has developed during the initial 78 week trial evidence of long QT syndrome, QTC interval ≥ 470 milliseconds (for male subjects) or ≥ 480 milliseconds (for female subjects), or torsades de pointes. Subjects with stable bundle branch block who exceed these limits for QTc interval are eligible for the trial if judged by the investigator not to be at increased risk for Torsades

The subject anticipates receiving any of the treatments listed in Table1.

The subject has developed a form of dementia that is not Alzheimer's disease, including but not limited to, dementia due to HIV infection, head trauma, vascular disease, Parkinson's disease, frontotemporal dementia, or Huntington's disease, as determined by the investigator.

INVESTIGATIONAL PRODUCT, DOSE, MODE OF ADMINISTRATION

Investigational Product:

MK-8931 will be supplied as tablets of 12 mg and 40 mg . All active doses from the initial 78 week trial will be carried forward into the long term safety trial, with all subjects on active treatment continuing on their same treatment arm. Subjects originally on placebo will be assigned to 40 mg:

TITLE OF TRIAL: A, Parallel-Group, Double Blind Long Term Safety Trial of MK-8931 in Subjects with Alzheimer's Disease. (Protocol No. MK-8931-017-21) (also known as SCH 900931, P07738)

1. MK-8931 12 mg orally once daily (QD) - 12/12 treatment group:
2. MK-8931 40 mg orally once daily (QD) - 40/40 and placebo/40 treatment groups:

STATISTICAL METHODS:

Data Sets to be Analyzed:

- The Full Analysis Set (FAS) population will serve as the primary population for the analysis of efficacy data in this trial.
- The All-Patients-as-Treated (APaT) population will be used for the analysis of safety data in this trial. The APaT population consists of all randomized subjects who received at least one dose of trial treatment, with subjects included in the treatment group corresponding to the trial treatment they actually received.
- It is noted that the first 200 subjects enrolled will be excluded from the primary efficacy and safety analyses, since the siDMC will have access to unblinded data from these subjects in advance of a dose decision.

Efficacy Analysis:

There are no formal hypotheses for this trial. All efficacy measurements analyzed during the initial 78 week trial will continue to be collected and analyzed in the long term safety trial. The primary endpoint is the 24-Month (6 months after the primary timepoint from the initial 78 week trial) change-from-baseline treatment difference on ADAS-Cog and ADCS-ADL.

Safety Analysis: Safety and tolerability will be assessed by a clinical review of all relevant parameters including adverse events (AEs), laboratory tests, vital signs, and ECG measurements.

[figure not shown]
Safety analyses will be conducted on the cumulative data from the initial 78-week trial pooled with the data from the long term safety trial; no analyses will be conducted on the long-term safety data alone.

The broad clinical and laboratory AE categories consisting of the percentage of subjects with any AE, with a drug related AE, with an SAE, with an AE which is both drug-related and serious, or who discontinued because of an AE are considered as Tier 2 endpoints and will be analyzed. Descriptive Safety Endpoints are considered as Tier 3 events and will also be analyzed.

Interim Analyses: There are no planned interim analyses for this long-term safety trial. (The Sponsor will be unblinded following the completion of the initial 78 week trial. Some Sponsor personnel will remain blinded during the long-term trial, as necessary, to support the conduct of the trial and the collection of efficacy data.)

2.1 Trial Design Diagram for Long Term Safety Trial

2.2 Trial Flow Chart for Long Term Safety Trial

Extension Trial Period: Visit Number (continuing from Initial 78 Week Trial)	Treatment															TC ^{d,f}	UV	ETV
	10B ^b	TC ^d	11	TC ^d	12	13	14	15	16	17	18	19	20	21	22			
Scheduled Week ^a (based on date of Randomization - in Initial 78 Week Trial)	78	80	82	86	91	104	130	156	182	208	234	260	286	312	338			
Extension Week (visual aid to show timing of visits in Long Term Safety Trial)	0	2	4	8	13	26	52	78	104	130	156	182	208	234	260			
Visit Window (Weeks)		+/-1	+/-1	+/-1	+/-1	+/-4	+/-4	+/-4	+/-4	+/-4	+/-4	+/-4	+/-4	+/-4	+/-4			
Informed Consent	X																	
Issue/Collect Subject Identification Card	X														X			
Record Concomitant Medication	X ^c		X		X	X	X		X		X		X		X	X	X ^e	X
Vital Signs	X ^c		X		X	X	X		X		X				X		X ^e	X
Body Weight	X ^c		X		X	X	X		X		X				X		X ^e	X
Directed Physical Exam	X ^c						X		X		X		X		X		X ^e	X
12-Lead Electrocardiogram	X ^c				X		X		X		X		X		X		X ^e	X
Skin Examination by Dermatologist																	X ^e	
Directed Skin Examination by Site Physician	X ^j						X		X		X		X		X		X ^e	
Hematology and Chemistry Samples	X ^c		X		X	X	X		X		X		X		X		X ^e	X
PK/PD Blood Samples ^k			X		X													
Urinalysis	X ^c		X		X	X	X		X		X		X		X		X ^e	X
Inclusion/Exclusion Criteria	X																	
ADAS-Cog					X	X	X		X		X		X		X			X
ADCS-ADL					X	X	X		X		X		X		X			X
CDR-SB					X	X		X		X		X		X				X
Mini-Mental State Examination (MMSE)						X	X		X		X		X		X			X

Extension Trial Period:	Treatment																		
Visit Number (continuing from Initial 78 Week Trial)	10B ^b	TC ^d	11	TC ^d	12	13	14	15	16	17	18	19	20	21	22	TC ^{d,f}	UV	ETV	
Scheduled Week ^a (based on date of Randomization - in Initial 78 Week Trial)	78	80	82	86	91	104	130	156	182	208	234	260	286	312	338				
Extension Week (visual aid to show timing of visits in Long Term Safety Trial)	0	2	4	8	13	26	52	78	104	130	156	182	208	234	260				
Visit Window (Weeks)		+/-1	+/-1	+/-1	+/-1	+/-4	+/-4	+/-4	+/-4	+/-4	+/-4	+/-4	+/-4	+/-4	+/-4				
Neuropsychiatric Inventory (NPI)						X	X		X		X		X		X			X	
Health Economic Assessment (HEA)						X	X		X		X		X		X			X	
Modified Resource Utilization in Dementia (RUD) Lite						X	X		X		X		X		X			X	
EuroQol Five Dimension Questionnaire (EQ-5D)						X	X		X		X		X		X			X	
Columbia Suicide Severity Rating Scale (C-SSRS)	X ^c		X		X	X	X	X	X	X	X	X	X	X	X		X ^e	X	
Structural Magnetic Resonance Imaging (MRI)																	X ^e		
Record Adverse Events		X	X	X	X	X	X	X	X	X	X	X	X	X	X	X	X	X	X
Dispense Trial Medication	X		X		X	X	X	X	X	X	X	X	X	X	X			X ^g	
Assess Medication Compliance			X		X	X	X	X	X	X	X	X	X	X	X			X	X
Drug Accountability Assessment			X		X	X	X	X	X	X	X	X	X	X	X			X	X
Ophthalmology Visit (details below)	X ⁱ						X											X ^e	
Visual Acuity	X ¹						X											X ^e	
Posterior Eye Exams	X ¹						X											X ^e	
Fundus Photography	X ¹						X											X ^e	
Fundus Autofluorescence ^h	X ¹						X											X ^e	
SD-OCT	X ¹						X											X ^e	

a Visits scheduled during the Long Term Safety Trial will be based off of the date of randomization in the Initial 78 Week Trial for subjects enrolling into the Long Term Safety Trial immediately following the completion of the Initial 78-week Trial. Subjects with a gap in study therapy between Visit 10 and Visit 10B will begin trial assessments for Visit 10B as noted in the flowchart and continue with the visit schedule as noted in the flowchart.

- b Visit 10 from the Initial 78 Week Trial and Visit 10B from the Long Term Safety Trial are considered a single visit and can be conducted on the same day. However, if waiting for test results from Visit 10B is necessary in the judgment of the investigator, Visit 10B procedures can be performed over more than one visit but ideally should not exceed a 2-week timeframe. Trial medication is to be dispensed on the last day of Visit 10B.
- c C-SSRS, ECG, directed Physical Exam, Recording of Concomitant Medications should be performed and Vital Signs, Body Weight and Laboratory samples (including urinalysis) should be collected for subjects with >3 month gap in therapy between Visit 10 and 10B. The timing of Visit 11 and all subsequent visits should be based on the trial dispensing date at Visit 10B.
- d Telephone contact with subject and trial partner/caregiver by site to assess safety, AEs, medication compliance, and any other issues. Any telephone contact may be conducted as an in-person unscheduled visit if the subject or caregiver expresses a preference for this or if the site has significant safety/tolerability concerns.
- e Procedures should be performed if clinically indicated as determined by the investigator.
- f Telephone contact will be performed 14 to 21 days after the final visit.
- g Drug dispensing may be performed at unscheduled visits at the discretion of the Investigator.
- h Best efforts will be made to accommodate the FAF assessment. FAF images will be read by a central Reading Center designated by the Sponsor.
- i Subjects who did not have a baseline ophthalmology examination completed during the initial 78 week trial or who have >6 month gap in study therapy between Visit 10 and 10B must have an ophthalmology examination completed during the Week 78 visit (10B) prior to dispensing trial medication.
- j Subjects who did not have a baseline dermatology examination completed during the initial 78 week trial or who have >6 month gap in study therapy between Visit 10 and 10B must have a dermatology examination completed during the Week 78 visit (10B) prior to dispensing trial medication.
- k Both plasma and dried blood spot (DBS) PK samples will be taken at each time point. The site will record the date and time of each PK sample and the date and time of the last two doses of trial medication before each PK sample. PK samples can be taken at the same time when blood samples for hematology and chemistry are taken.

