7.3.2 Subject Exclusion Criteria

A subject meeting any of the exclusion criteria listed below must be excluded from participating in the trial. Subject

1. is at imminent risk of self-harm, based on clinical interview or on the Columbia Suicidality Severity Rating Scale (C-SSRS), or of harm to others in the opinion of the investigator. Subjects must be excluded if they report suicidal ideation with intent, with or without a plan (eg, suicidal ideation item 4 or 5 on the C-SSRS) in the past 1 month or suicidal behavior in the past 6 months.
2. has developed a recent or ongoing, uncontrolled, clinically significant medical condition (such as, but not limited to, diabetes, hypertension, thyroid or endocrine disease, congestive heart failure, angina, cardiac or gastrointestinal disease,

dialysis, or abnormal renal function with estimated creatinine clearance < 30 mL/min) other than Alzheimer's disease such that, in the judgment of the investigator, participation in the trial would pose a significant medical risk to the subject. Controlled co-morbid conditions (including diabetes, hypertension, heart disease, etc) are not exclusionary if stable. All concomitant medications, supplements, or other substances must be kept as stable as medically possible during the trial.

Note: urinary tract infections at Visit 10B are not exclusionary if adequately treated (as documented by repeat urinalysis).

3. has a history of, or has developed during the initial 78 week trial evidence of long QT syndrome, QTC interval ≥ 470 milliseconds (for male subjects) or ≥ 480 milliseconds (for female subjects), or torsades de pointes.
4. anticipates receiving any of the treatments listed in **Table 1** during the study.

Table 1 Prohibited Medications, Supplements, and Other Substances
Anti-amyloid agents (eg, tarenflurbil, tramiprosate)
Anti-amyloid antibodies (eg, bapineuzumab)
Anti-amyloid vaccine (Subjects who received placebo in a vaccine trial may participate in this trial.)
CYP3A4 inducers (strong) including: rifampicin and St. John's Wort, phenytoin, carbamazepine Exceptions: Use of the following is acceptable: topical use; short-term (<2 weeks) oral treatment during the trial; use of oral St. John's Wort <300 mg three times a day during the trial, regardless of duration.

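### The Visit 10B C-SSRS is required only after a gap of more than 3 months, so after a shorter gap drug can be dispensed with no required C-SSRS covering the time since Visit 10

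*Combined protocol and SAP*

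**What the plan says.** Exclusion 1 (Section 7.3.2, also in the synopsis) bars subjects at imminent risk of self-harm, judged by clinical interview or by the C-SSRS. It then sets look-back periods for what subjects report: "suicidal ideation item 4 or 5 on the C-SSRS) in the past 1 month or suicidal behavior in the past 6 months".

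Section 7.6, item 9, leaves the timing of the C-SSRS to the flow chart, with extra use at unscheduled visits if clinically indicated. In the flow chart (Section 2.2), the Visit 10B cell of the C-SSRS row carries footnote c. That footnote opens "C-SSRS, ECG, directed Physical Exam, Recording of Concomitant Medications should be performed" and then says that vital signs, weight and laboratory samples "should be collected for subjects with >3 month gap in therapy between Visit 10 and 10B". The inclusion/exclusion row at 10B has no footnote.

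On timing, footnote b says that Visits 10 and 10B "are considered a single visit and can be conducted on the same day". It allows 10B to be spread over about 2 weeks while test results are awaited, with drug dispensed on its last day. Longer delays are foreseen in footnote a: "Subjects with a gap in study therapy between Visit 10 and Visit 10B will begin trial assessments". Footnote c adds: "The timing of Visit 11 and all subsequent visits should be based on the trial dispensing date at Visit 10B".

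**The concern.** The protocol already accepts that a break in therapy can call for a repeat C-SSRS before the extension starts. It sets the trigger at 3 months, the same as for the ECG, laboratory samples and physical examination. But the C-SSRS is the instrument named in an eligibility rule that has its own 1-month window. A subject who returns after, say, 2 months can receive drug without anyone being required to ask the structured questions for the interval since Visit 10.

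Two features give this some weight. First, routine adverse-event questioning is deliberately general and should not prompt for specific events (Section 7.7.2.3.1). That section names the C-SSRS and the NPI as other sources of information, and the first NPI in the extension is at Visit 13. Second, for the placebo/40 group the dose after Visit 10B is the first active dose; for the other groups it is a restart. A positive item 4 or 5 leads to same-day mental health evaluation (Section 7.6, item 9), and that trigger is not applied systematically if the scale is not given.

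**Working it through.** The plan states no figure on this point, so the check places the timings side by side.

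**Inputs**
- Look-back for ideation with intent: 1 month (exclusion 1).
- Trigger for a C-SSRS at 10B: gap of more than 3 months (footnote c).
- Next required C-SSRS: Visit 11, extension week 4, window ±1 week, counted from dispensing (flow chart, footnote c).
- Required C-SSRS visits after that: extension weeks 13, 26, 52 and every 26 weeks to 260.
- Assumptions: a C-SSRS was done at Visit 10 (the schedule of the initial trial is not in the documents), and the therapy gap equals the time from Visit 10 to dispensing.

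**Conversion.** 1 month = 365.25 / 12 / 7 = 4.35 weeks, so 2 months = 8.7 weeks and 3 months = 13.0 weeks. Trigger / look-back = 3 / 1 = 3.

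**Share of the look-back that falls after Visit 10.** With a gap of g weeks, the share is g / 4.35, up to a maximum of 1.

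| Gap | Age of Visit 10 C-SSRS at dispensing | Share of look-back after Visit 10 | C-SSRS required at 10B? |
|---|---|---|---|
| Same day | 0 | 0 | No |
| 2 weeks | 2 weeks | 2 / 4.35 = 0.46 | No |
| 3 weeks | 3 weeks | 3 / 4.35 = 0.69 | No |
| 1 month | 4.3 weeks | 1 | No |
| 2 months | 8.7 weeks | 1 | No |
| 3 months | 13.0 weeks | 1 | No |
| Over 3 months | over 13.0 weeks | 1 | Yes |

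Between 1 and 3 months, the Visit 10 assessment lies wholly outside the window. Below 1 month it is dated inside the window, but it cannot detect ideation that begins afterwards.

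**After dispensing.** The next required C-SSRS comes at 4 − 1 = 3 to 4 + 1 = 5 weeks. The longest stretch from Visit 10 to a required C-SSRS is about 13.0 + 5 = 18.0 weeks.

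**Spacing on drug, for comparison.** 13 − 4 = 9 weeks, 26 − 13 = 13 weeks, then 26 weeks for (260 − 26) / 26 = 9 intervals.

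**Does the 3-month condition govern the C-SSRS?** Footnote c has two verbs, so the condition could be attached only to the collected items (vital signs, weight, samples). That reading is weaker. The C-SSRS cell carries the same footnote mark as those items, and a C-SSRS meant for everyone would need no footnote, as the eligibility row shows. The summary of changes also explains the whole list by reference to subjects with an extensive gap.

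**The case against.** The strongest reply is that the two periods measure different things. One month is a recall period for what a subject reports; 3 months is a length of interruption that triggers a repeat safety work-up. Nothing says they must agree, and exclusion 1 also has a 6-month look-back for behavior. The eligibility review at 10B is unconditional and must address both periods as of that visit. Clinical interview is an accepted basis, and items 4 and 5 are given only as an example. This stands: no stated requirement is breached.

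A second reply is that a trigger of 1 month would be equally arbitrary, because a Visit 10 assessment is silent on anything that starts later. This also stands, and it is why the main proposal below depends on whether dispensing is on the day of Visit 10 rather than on either look-back.

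A third is that the ECG and laboratory items inform exclusions too (QTc, creatinine clearance) and keep the 3-month trigger. That is a fair point about consistency. The C-SSRS differs in being a short questionnaire that needs no equipment or sample, and in being named in a criterion with a 1-month window.

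Other safeguards exist: the Week 2 telephone contact, an unscheduled C-SSRS if indicated, and reporting of suicidal ideation or behavior as an event of clinical interest (Section 7.7.2.2.3). None requires the scale before dispensing. The suicidality guidance document and the Manual of Assessments are not available here and may contain further instructions to sites.

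**Conclusion.** The point holds as a minor improvement to safety screening. After a gap of 3 months or less, no required C-SSRS covers the time since Visit 10 before drug is dispensed. For gaps of 1 to 3 months, none falls within the 1-month look-back at all. The latter finding does not depend on whether a C-SSRS was done at Visit 10.

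A reader might infer that exclusion 1 is not enforced after a shorter gap, or that the protocol contradicts itself. The documents do not support this: the review at 10B applies to every subject, and an interview suffices. A reader might also infer that the interval between C-SSRS assessments is itself unsafe. That does not follow either, since the plan accepts 26 weeks on drug from Visit 13 on, longer than the 18.0-week maximum found here. The issue is only the absence of a required structured instrument before the first or restarted dose.

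The number of subjects with a delayed 10B is not stated. It could be small, and for gaps of 1 to 3 months it could be zero. Endpoints, power and alpha are unaffected.

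**What to change.** Amend footnote c to require a C-SSRS at Visit 10B, before study drug is dispensed, whenever dispensing at 10B is not on the same day as Visit 10. At minimum, require it for any gap of 1 month or more, accepting that this leaves shorter delays uncovered. Keep the trigger of more than 3 months for the ECG, laboratory samples and other footnote c items. Footnote j already has a suitable form of words on sequence: such subjects "must have a dermatology examination completed during the Week 78 visit (10B) prior to dispensing trial medication".

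The cost is one footnote, plus one short questionnaire already used in the trial for each subject whose dispensing is delayed. That includes subjects who wait up to about 2 weeks for test results under footnote b; the 1-month minimum would spare them. Subjects who have both visits and dispensing on one day are unaffected under either version.
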